#### Figure 1. Study Design.

Abbreviations: FPI = first patient in; LPI = last patient in

## 3.2 Study Sites

Eligible patients will be selected from over 12 sites in Germany and approximately 28 sites in the US. A feasibility study will be conducted as part of the site activation process to ensure optimal nivolumab prescribing patterns and large volumes of patients given the relatively low prevalence of these diseases. After the feasibility assessment, sites with representative medical practices, geographical diversity, and epidemiological data describing the variety of real-life aspects of EC or GEJC treatment will be included in this study. Patient selection will be based on systematic sampling technique, i.e., all consecutive eligible patients are expected to be included in the study.

# 3.3 Study Population

### 3.3.1 Inclusion Criteria

To be enrolled in the study patients must meet the following criteria:

- 1. Patients aged 18 years or older at the time of informed consent
- 2. Patients provide voluntary informed consent to participate in the study before inclusion in the study
- 3. Confirmed diagnosis of resected early-stage (Stage II/III) EC or GEJC (histologically or cytologically confirmed stage)
- 4. Physician decision to treat the patient with adjuvant nivolumab (according to the local label as per country-specific regulations) must be made prior to and independently of participation in the study

## 3.3.2 Exclusion Criteria

Patients that meet one or more of the following criteria will not be enrolled in any component of the study:

- 1. Participation in a clinical trial of an investigational drug, concurrently or within the last 30 days (patients who have completed their participation in an interventional trial and who are only followed-up for OS can be enrolled)
- 2. Prior treatment with immuno-oncologic agents including nivolumab for any indication
- 3. Patients with a current primary diagnosis of a cancer other than EC or GJEC that requires systemic or other treatment, or has not been treated curatively (as per discretion of the investigator)

# 3.4 Data Collection Process

## 3.4.1 PRO Instruments

PROs will be collected in the context of this study. Specifically, the validated Cancer Therapy Satisfaction Questionnaire (CTSQ) will be self-administered in a paper format in the primary languages spoken at study sites. The CTSQ is a self-administered questionnaire that assesses patient satisfaction with and preference for chemotherapy, hormonal therapy, and biological therapies orally (pill) and/or via intravenous administration within the past four weeks.

Patients will be asked to complete the self-administered CTSQ once per visit and at the time points defined in the protocol until nivolumab discontinuation, the end of study period, death, lost to follow-up, or withdrawal, whichever comes first.

Additionally, the validated Functional Assessment of Cancer Therapy – General 7 (FACT-G7) will be evaluated in this study. The seven-items included in this questionnaire are GP1 "I have lack of energy", GP2 "I have pain", GP3 "I have nausea", GP4 "I worry that my condition will get worse", GP5 "I am sleeping well", GP6 "I am able to enjoy my life", and GP7 "I am content with the quality of my life right now". Patients will be asked to complete the self-administered FACT-G7 once per visit and at the time points defined in the protocol until nivolumab discontinuation, the end of study period, death, lost to follow-up, or withdrawal, whichever comes first.

Since HR-QoL of patients in the real-world setting is likely to be adversely affected by recovery from surgery, specific questions around recovery from surgery will be included in the eCRF to minimize confounding of HR-QoL data.

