## 3 STUDY DESIGN

### 3.1 Overview of Study Design

This is a non-interventional, prospective, multinational, multicenter, post-marketing observational study designed to describe the real-world effectiveness and patterns of use of adjuvant nivolumab in patients with early stage (Stage II/III) EC or GEJC. This study will be conducted in the US and Germany will collect data available from patients' medical files and other items routinely collected during disease management in clinical practice and patient-reported outcomes (PRO) related to treatment satisfaction and quality of life.

This study is strictly observational and does not result in interference with standard medical care; thus, it will not impact the treatment of study participants. Prescriptions of nivolumab will be at

the sole discretion of the treating physician. Patients are to be enrolled into this noninterventional, primary data collection study no earlier than the decision to initiate treatment with nivolumab and no later than the first dose of nivolumab treatment. It is mandatory that the treating physician's decision to start treatment with nivolumab for early-stage EC or GECJ is taken independently and before the decision to invite the patient to participate in the study. Day 0 corresponds to the day of nivolumab initiation (administration of the first dose of treatment). The local investigator is responsible for the exact procedures of administration of nivolumab, and concomitant medications and therapies deemed necessary for the supportive care and safety of the patients.

Once the decision to prescribe nivolumab is taken by the medical team/physicians according to usual practice, patients will be screened for selection criteria. If the patient meets all inclusion criteria and none of the exclusion criteria, the investigator should then invite the patient to participate in the study and collect their consent to participate. Enrollment in the study is then clearly distinguished from the therapeutic decision to initiate nivolumab.

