## 3.5.1.5 Patient-reported Outcome

In this study, patient satisfaction with nivolumab treatment will be assessed using the CTSQ at baseline and at the visits indicated in **Table 5**. In addition, three items form the FACT-G questionnaire will be assessed at baseline and at visits indicated in **Table 5**. Patient-reported outcomes will only be collected for 12 months, which is the treatment duration for nivolumab.

PRO	Definition	Timing
CTSQ	The revised CTSQ is 16-item instrument measuring three domains: Expectations of Therapy (5 items), Feelings about Side Effects (4 items), and Satisfaction with Therapy (7 items).	Day 0, and Months 3, 6, 9, and 12
FACT-G7	GP1 "I have lack of energy"	Day 0, and
	GP2 "I have pain"	Months 3, 6, 9, and 12
	GP3 "I have nausea"	
	GP4 "I worry that my condition will get worse"	
	GP5 "I am sleeping well"	
	GP6 "I am able to enjoy my life"	
	GP7 "I am content with the quality of my life right now"	

Table 5. Cancer Therapy Satisfaction Questionnaire

Abbreviations: CTSQ=Cancer Therapy Satisfaction Questionnaire; FACT-G7=Functional Assessment of Cancer Therapy – General 7

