# 4.1.4 Analysis Plan for Exploratory Objectives

PRO analysis of patient satisfaction with nivolumab treatment will be assessed using CTSQ and FACT-G7 instrument. CTSQ scores results overall and for each of the three domains: Expectations of Therapy (five items), Feelings about Side Effects (four items), and Satisfaction with Therapy (seven items) will be summarized using standard descriptive statistics (see Section 4.1.2). The FACT-G7 will include items GP1 "I have lack of energy", GP2 "I have pain", GP3 "I have nausea", GP4 "I worry that my condition will get worse", GP5 "I am sleeping well", GP6 "I am able to enjoy my life", and GP7 "I am content with the quality of my life right now", and will be summarized using standard descriptive statistics (see Section 4.1.2).

Data will be recorded at Day 0, and Months 3, 6, 9, and 12 (counted relative to treatment initiation). Mean change from Day 0 to assessment points throughout the study will be evaluated. At each timepoint for analysis, the number of patients who completed the patient satisfaction questionnaire and the FACT-G7 will be reported as a percentage of eligible patients.

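### FACT-G7 collection ends at nivolumab discontinuation in one section and runs to Month 12 in another; under the first rule the change from Day 0 describes only patients still on drug, and the Day 0 CTSQ cannot measure satisfaction with nivolumab

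*Protocol*

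**What the plan says.** Section 3.4.1 gives both questionnaires the same end of collection. For quality of life: "Patients will be asked to complete the self-administered FACT-G7 once per visit and at the time points defined in the protocol until nivolumab discontinuation". For satisfaction: "Patients will be asked to complete the self-administered CTSQ once per visit and at the time points defined in the protocol until nivolumab discontinuation". In both cases end of study, death, loss to follow-up or withdrawal ends collection if it comes first.

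Section 3.5.1.5 states a different limit: "Patient-reported outcomes will only be collected for 12 months, which is the treatment duration for nivolumab". Table 5 lists Day 0 and Months 3, 6, 9 and 12 for both instruments and does not mention discontinuation. Section 4.1.4 repeats that schedule and adds: "Mean change from Day 0 to assessment points throughout the study will be evaluated". It also reports completion as a share of eligible patients, without defining who is eligible once nivolumab has stopped.

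On the baseline, section 3.1 says "Day 0 corresponds to the day of nivolumab initiation (administration of the first dose of treatment". The CTSQ, as section 3.4.1 describes it, concerns therapy taken "orally (pill) and/or via intravenous administration within the past four weeks". Section 3.3.2 excludes anyone with earlier nivolumab. Section 3.5.1.5 nevertheless presents the baseline CTSQ as part of assessing satisfaction with nivolumab. The same section says "three items form the FACT-G questionnaire will be assessed at baseline", whereas section 3.4.1, Table 5 and section 4.1.4 all list seven FACT-G7 items.

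**The concern.** FACT-G7 is a general quality-of-life measure covering energy, pain, nausea, worry, sleep, enjoyment and contentment. None of these items requires the patient to be on treatment. If the form is withdrawn when nivolumab stops, the patients who leave the sample include those who progressed or had toxicity, and their quality of life is likely to differ from that of patients who continue. The trend from Day 0 to Month 12 would then mix real change with a change in who is answering. No later analysis can restore forms that were never requested, so this belongs in the protocol rather than the SAP.

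For the CTSQ, a change score is meaningful as satisfaction with nivolumab only if both ends refer to nivolumab. The Day 0 end does not. Reported under the label used in section 3.5.1.5, it would be misread.

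**Working it through.** The plan states no figure for this point, so the check is a comparison of sections plus an illustration of how many patients could be affected.

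**Step 1: the two collection rules.** Take a patient who stops nivolumab at Month 4 and is alive and attending at Months 6, 9 and 12. Under section 3.4.1 no further FACT-G7 is requested. Under Table 5 three more are. A site cannot tell from the protocol which applies.

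**Step 2: is leaving the sample related to quality of life?** Table 3 lists the reasons for discontinuation: death, disease progression, drug-related and other toxicity, patient request, pregnancy, loss to follow-up and other. Several of these plausibly go with poorer scores; some need not. The direction is therefore probable rather than certain.

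**Step 3: how many patients could be off drug by Month 12?** Assume constant-hazard DFS and, for illustration only, that nivolumab stops at recurrence. The inputs are:

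- Median DFS on nivolumab in the reference trial: 22.4 months, 95% CI 16.6 to 34.0 (section 1.1), giving S(t) = exp(-ln 2 × t / 22.4).
- Planning DFS of 40% at 24 months (section 4.2), giving S(t) = 0.40^(t/24).

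| Month | Event-free, median 22.4 months | Event-free, 40% at 24 months |
|---|---|---|
| 3 | 91% | 89% |
| 6 | 83% | 80% |
| 9 | 76% | 71% |
| 12 | 69% | 63% |

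At Month 12, exp(-ln 2 × 12 / 22.4) = 0.690 and 0.40^(12/24) = 0.632. The share with recurrence or death is 1 - 0.690 = 31% to 1 - 0.632 = 37%, or about 97 to 115 of 314 patients. At the CI limits of 34.0 and 16.6 months the share is 22% and 39%.

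Toxicity and other stops add to this. If a further 10% to 20% of event-free patients have stopped early (an assumption), the share off drug runs from 1 - 0.690 × 0.90 = 38% to 1 - 0.632 × 0.80 = 49%.

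**Step 4: the effect on the mean.** Let f be the share of the relevant cohort off drug and D the amount by which their mean change is worse than that of patients on drug. The on-drug mean exceeds the cohort mean by f × D. The protocol gives no value for D, no FACT-G7 scale range and no meaningful difference. It also gives no split of DFS events into recurrences and deaths, so f among survivors is unknown. The product cannot be computed.

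**Step 5: the CTSQ baseline.** Day 0 is the first dose, the recall window is the preceding four weeks, and earlier nivolumab is an exclusion. The Day 0 answers must therefore refer to some other therapy or to none. The scores from Months 3 to 12, collected on treatment, do concern nivolumab.

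**The case against.** The strongest reply is that the two rules can be read together, with 12 months as an upper limit and discontinuation as an earlier stop. An on-treatment description is a legitimate target, since section 1.2 asks about quality of life and satisfaction in connection with nivolumab treatment. That reading is possible, but the protocol does not state it. Section 2.3 names quality of life without restricting it to time on drug, and section 4.1.4 describes change across the study. If an on-treatment summary is meant, it has to be labelled as one.

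A reader might infer that quality of life would come only from patients doing well. The protocol does not support that. Day 0 forms come from all respondents, patients on drug can have toxicity and poor scores, and some stop for unrelated reasons. The accurate description is that post-baseline data come from patients still on nivolumab.

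A reader might also infer that the CTSQ is analysed only as change. Section 4.1.4 first summarises the overall and domain scores descriptively, and the synopsis shows that a measurement before nivolumab is intended. Only the Day 0 value and the change score fail as measures of satisfaction with nivolumab. Stopping the CTSQ at discontinuation suits a questionnaire about current therapy.

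Section 3.4.1 collects questions on recovery from surgery that section 4.1.4 does not mention. That is not a defect here: section 4.1.1 leaves procedures for controlling bias to the SAP, and the choice of a longitudinal model belongs there too.

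Finally, no visits are mandatory (sections 3.1 and 3.4.2), so some forms after discontinuation will be missing, perhaps informatively. This limits how much of the selection the change can remove, but does not argue against asking.

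**Conclusion.** The concern stands in a limited form. Sections 3.4.1 and 3.5.1.5 must be reconciled on when FACT-G7 collection ends. Under the section 3.4.1 rule, post-baseline change is conditional on still receiving nivolumab and probably flatters the later time points. The group potentially affected is substantial: 31% to 37% with recurrence or death by Month 12, assuming a constant hazard and that nivolumab stops at recurrence, before other stops are counted. Part of that share is deaths, which no collection rule recovers. Any figure for the bias in FACT-G7 points would rest on assumed inputs, so none is given.

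The CTSQ point is one of labelling: Day 0, and change from it, are not satisfaction with nivolumab. The count of three FACT-G items is a slip, since every list in the protocol has seven.

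Severity is minor. The objective is exploratory, the study tests no hypotheses, and the primary DFS estimate is unaffected.

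**What to change.** - In section 3.4.1, ask for FACT-G7 at every attended data-collection point through Month 12 regardless of nivolumab status, and bring section 3.5.1.5 and Table 5 into line. CTSQ collection may still end at discontinuation, stated in both places.
- In section 4.1.4, present FACT-G7 results by on and off nivolumab, and define the completion denominator on that basis, so that patients who stop do not drop out of the count.
- In section 3.5.1.5, describe the Day 0 CTSQ as context before nivolumab. Use the Month 3 to 12 scores to answer the satisfaction objective, and do not present change from Day 0 as satisfaction with nivolumab.
- Correct the number of FACT-G items in section 3.5.1.5 from three to seven.

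The cost is protocol wording and at most four additional seven-item forms (Months 3, 6, 9 and 12) for a patient who stops early. Because attendance follows routine care, some of these forms will be missing, and the completion table should show that.

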## 3.4.2 Patient Data

eCRF will be used by study investigators or qualified research staff members to enter data into the electronic database capture (EDC) system. As part of the routine care, study investigators will evaluate or ask patients about their disease history, treatment history, and any AEs experienced since the previous clinical visit and the related information. AEs will be collected according to guidelines and timelines in Section 7.1.1.

As this is a non-interventional study, mandatory assessments will not be required from the study sites or patients. However, data collection/reporting will be conducted in a consistent way among different sites/countries whenever possible to avoid bias in the data collection process. Data will

be entered by all sites into eCRFs, with monitoring for source data verification. Data will be collected from eCRFs, which are to be completed by site staff. Patients will report treatment satisfaction via paper-based or electronic-based, validated questionnaires.

## 3.5 Definitions of Study Variables

#### 3.5.1 Outcome Variables

### 3.5.1.1 Clinical Outcomes

**Table 1** presents the definitions of the clinical outcome variables and **Table 2** presents definitions of clinical primary and secondary effectiveness outcomes that will be continuously evaluated as part of the study in all nivolumab patients and in patients that receive subsequent treatment(s) following nivolumab treatment.

Outcomes	Type of variables	Definition
Disease progression	Categorical	Disease progression will be evaluated at each available tumor assessment, which is collected either at first assessment after initial treatment' or during follow-up:
		Investigator assessed:
		
 
Disease progression = Yes, if best therapy tumor response = disease progression
 

		
 
Disease progression = No, if best therapy tumor response = complete/ near complete response, tumor shrinkage or mixed response
 

		• Per RECIST  :
		
 
Disease progression = Yes, if best therapy tumor response = PD
 

		
 
Disease progression = No, if best therapy tumor response=CR, PR, or SD
 

Recurrence	Categorical	Recurrence is defined as the detection of relapse of neoplastic disease during follow-up after nivolumab treatment initiation as assessed by the investigator
Type of recurrence (local/regional, metastatic)	Categorical	• Local recurrence is defined as a cancer that after treatment reappears at the primary site, i.e., at the site where it originated.
		• Regional recurrence is defined as cancer that reappears after treatment in the lymph nodes or tissues near the primary site.
		• Metastatic (distant) recurrence is defined as cancer that spreads (metastasizes) after treatment to distant organs or tissues such as the brain, kidneys, lungs, liver, or bone marrow.

Table 1. Clinical Outcomes Definition

Abbreviations: CR=Complete Response; PD=Progressive Disease; PR=Partial Response; SD=Stable Disease

Table 2: Primary and Secondary	Effectiveness	Outcomes Definition
---------------------------------------	---------------	----------------------------

Outcomes Type of variables	Definition
----------------------------	------------

Effectiveness outcomes in pati	ients initiating adju	uvant nivolumab treatment
DFS	Time-to-event	Time between initiation of nivolumab treatment and the first date of recurrence (local, regional, or distant from the primary resected site) or death from any causes, whichever occurs first, as assessed by the investigator prior to subsequent anti-cancer therapy.
DFS rates	Continuous	DFS rates are defined as the probability that a patient is alive and presents no signs of recurrence at specific time points, following adjuvant nivolumab initiation.
08	Time-to-event	Time between initiation of nivolumab treatment until date of death due to any cause. Patients who are alive at last visit will be censored on date last known to be alive.
OS rates	Continuous	OS rates are defined as the probability that a patient is alive at specific time points, following adjuvant nivolumab initiation.
DMFS	Time-to-event	Time between initiation of nivolumab treatment and date of appearance of distant metastasis or death from any causes, whichever occurs first, as assessed by the investigator prior to subsequent anti-cancer therapy.
DMFS rates	Continuous	DFS rates are defined as the probability that a patient is alive and presents no signs of metastasis at specific time points, following adjuvant nivolumab initiation.
Time to recurrence	Continuous	Time between initiation of nivolumab treatment and the first date of recurrence.
Recurrence rates	Categorical	Recurrence rates are defined as disease recurrence (i.e., local/regional, metastatic) at specific time points, following adjuvant nivolumab initiation.
PRS	Time-to-event	PRS is defined as the interval from the date of any recurrence to the date of death from any cause. Patients who are alive at last visit will be censored on date last known to be alive.
Effectiveness outcomes in pati discontinuation:	ients that receive s	ubsequent treatment(s) following adjuvant nivolumab
OS of subsequent treatment	Time-to-event	Time between initiation of subsequent treatment until date of death due to any cause. Patients who are alive at last visit will be censored on date last known to be alive.
OS rates of subsequent treatment	Continuous	OS rates are defined as the probability that a patient is alive at specific time points, following subsequent treatment initiation.
PFS2	Time-to-event	Time between initiation of subsequent treatment and date of disease progression or death if occurred before progression. In case of censored event, the duration of response is censored on the date of last tumor assessment or enrollment (whichever occurs last)
PFS2 rates	Continuous	PFS2 rates are defined as the probability that a patient is alive and presents no signs of disease progression at specific time points, following subsequent treatment initiation.
ORR of subsequent treatment	Continuous	Total number of patients with CR or PR to subsequent treatment divided by the total number of patients.

Abbreviations: CR = Complete Response; DFS = Disease-Free Survival; DMFS = Distant Metastasis-Free Survival; OS = Overall Survival; ORR = Overall Response Rate; PFS2 = Progression-Free Survival 2; PR = Partial Response; PRS = Post-Recurrence Survival

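### Table 1 codes disease progression from best response, so as written it misses progression after an initial response or stable disease and would bias PFS2 upward if PFS2 uses that flag

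*Protocol*

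**What the plan says.** Section 3.5.1.1, Table 1 defines disease progression as a categorical variable. The row opens with "Disease progression will be evaluated at each available tumor assessment". Two pairs of coding lines follow.

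- RECIST: "Disease progression = Yes, if best therapy tumor response = PD" and "Disease progression = No, if best therapy tumor response=CR, PR, or SD".
- Investigator-assessed: "Disease progression = Yes, if best therapy tumor response = disease progression" and "Disease progression = No, if best therapy tumor response = complete/ near complete response, tumor shrinkage or mixed response".

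Table 2 defines PFS2 as "Time between initiation of subsequent treatment and date of disease progression or death if occurred before progression". Patients without an event are censored at the later of the last tumour assessment and enrollment. For the rates, "PFS2 rates are defined as the probability that a patient is alive and presents no signs of disease progression at specific time points".

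Section 3.5.1.2, Table 3 lists, among the items for all visits, progression as Yes/No (by investigator or RECIST), a date of progression, and the imaging used with its assessment date. It gives no further rule for deciding Yes or No. Median PFS2 and PFS2 rates are secondary outcomes (Synopsis; section 2.2), with Kaplan-Meier analysis planned in sections 4.1.1.2 and 4.1.3.1.

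**The concern.** The opening sentence of the Table 1 row and its coding lines describe different variables. The first is a status that can change from scan to scan. The second is a summary over the whole of a therapy that can only stay the same or improve. Progression after a period of disease control is an event that PFS2 exists to capture, and the coding lines cannot register it.

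Table 1 holds the protocol's only coding rule for progression. A programmer or abstractor who follows the coding lines records No for a late progressor, while one who follows the opening sentence records Yes. At stake are PFS2, PFS2 rates and any summary of progression in patients who receive subsequent treatment. The error under the coding lines always runs towards longer PFS2.

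There is a second gap in the same row. The RECIST list of non-progression includes SD, but the investigator list has no stable category, so a stable patient gets neither Yes nor No. Section 5.1 expects that not all physicians will use RECIST 1.1, so the investigator branch will be needed.

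**Working it through.** **Step 1: apply the rule to response sequences.** This needs no assumptions.

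| Sequence on subsequent treatment | Best response | Table 1 code | Progressed? |
|---|---|---|---|
| PD at first assessment (with or without further PD) | PD | Yes | Yes |
| SD, then PD | SD | No | Yes |
| PR, then PD | PR | No | Yes |
| CR, then PD | CR | No | Yes |
| Stable throughout, investigator-assessed | stable | none | No |

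**Step 2: carry the code into PFS2.** If the PFS2 event comes from this flag, patients in rows 2 to 4 have no event at progression. They have one at death, or are censored at the last tumour assessment. Both lengthen estimated PFS2.

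**Step 3: illustrate the size.** The protocol gives no PFS2 figure to reproduce and none of the inputs needed. All inputs below are assumed.

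*Illustration A (closed form, no censoring).* A share c of patients has disease control. The other 1 − c progress between 0.5 and 2.5 months and are coded Yes under either reading. Controlled patients progress at 2 months plus an exponential time with median 6, then die after a further exponential time with median 6.

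- Per-assessment coding: the median solves c·2^(−(t−2)/6) = 0.5, so t = 2 + 6·log2(2c).
  - c = 0.65: 2 + 6 × 0.3785 = 4.3 months.
  - c = 0.80: 2 + 6 × 0.6781 = 6.1 months.
- Best-response coding (controlled patients have an event only at death): c·(1 + y)·e^(−y) = 0.5, with y = (ln 2 / 6)(t − 2).
  - c = 0.65: y = 0.909, t = 9.9 months.
  - c = 0.80: y = 1.305, t = 13.3 months.
- 12-month PFS2: c × 2^(−10/6) = 0.315c gives 20% and 25%. The best-response rule gives 0.679c, that is 44% and 54%.
- Median survival after progression of 2 to 3 months instead of 6: the medians under the rule fall to 6.8–7.7 months (c = 0.65) and 9.0–10.2 months (c = 0.80).

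*Illustration B (simulation, 20,000 patients per scenario).* Exponential time to first event, 10% of first events being deaths, assessments every 3 months, administrative censoring at 24 months. Progression is coded Yes under the rule only if found at the first assessment.

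| Assumed median to first event (months) | Assumed median survival after progression (months) | KM median PFS2, per assessment | KM median PFS2, best response | Detected progressions coded No |
|---|---|---|---|---|
| 4 | 4 | 6.0 | 6.5 | 59% |
| 4 | 8 | 6.0 | 7.6 | 58% |
| 6 | 4 | 6.0 | 9.9 | 69% |
| 6 | 8 | 6.0 | 12.4 | 68% |
| 8 | 4 | 9.0 | 12.6 | 74% |
| 8 | 8 | 9.0 | 16.3 | 74% |

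The per-assessment medians fall on multiples of 3 because progression is dated at the 3-monthly assessment that finds it. The direction is the same in every scenario. The shift ranges from 0.5 months to about 7 months.

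**The case against.** The strongest reply is that the bias depends on one reading. A best response over a whole therapy cannot be evaluated afresh at each assessment, so the term may be loose wording for the response at that assessment. Table 3 also collects a progression date separately, Table 1 defines a Yes/No flag and no date, and PFS2 runs to a date. Nothing states that this date is derived from the flag. This stands: if the sponsor codes each assessment's own response, or uses the recorded date directly, PFS2 is not biased. It does not remove the contradiction, because no other rule says what counts as progression and no text ties PFS2 to the Table 3 date.

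A reader might also infer that PFS2 turns into overall survival for patients with disease control. The documents do not support that: Table 2 censors PFS2 at the last tumour assessment or enrollment, but OS at the date last known alive, so the two differ for patients still alive. Nor is it right that only a single, isolated PD result is coded Yes; repeated PD with nothing better is coded Yes too.

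Finally, the study is descriptive, with no hypothesis tests. DFS rests on investigator-assessed recurrence, which Table 1 defines separately, and the sample size rests on DFS. OS, DMFS, PRS and ORR do not use the flag. All of this stands and limits the weight of the point.

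**Conclusion.** The rule is wrong as written and should be fixed. Table 1 contradicts itself, its coding lines cannot identify progression after CR, PR or SD, and the investigator list omits stable disease. These conclusions follow from the text alone.

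The effect on PFS2 is conditional. If PFS2 is derived from the flag, PFS2 and PFS2 rates are biased upward; if the recorded progression date is used, they are not. A reader might take a doubling of median PFS2 as the expected effect. The protocol does not support any particular size: on assumed inputs the shift runs from about 6.0 to 6.5 months up to about 6.1 to 13.3 months. The damage is confined to PFS2, its rates and any progression summary; the primary outcome is untouched.

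**What to change.** 1. In all four coding lines of Table 1, replace the best-response term with the tumour response at that assessment.
2. Add stable disease to the investigator-assessed list for no progression.
3. In Table 2, state that the PFS2 event date is the first recorded date of progression (RECIST PD or investigator-assessed, as collected under Table 3) after the start of subsequent treatment, or death if that comes first.
4. Keep best response for ORR only.

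The cost is a protocol wording change and the matching derivation. One check is needed: Table 3 lists progression Yes/No, its date and the imaging assessment date, but no CR/PR/SD/PD item per visit. The sponsor should confirm that the eCRF records the response at each assessment, and add the item if it does not.
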